6.1.2 Study Procedures

6.1.2.1 Screening Period

The following procedures will be performed within 14 days of study vaccination. The Screening visit and Day 0 visit may be combined, if feasible, at any given study site. Screening information collected as part of a standard-of-care protocol prior to informed consent form (ICF) signing may be used if collected during the same healthcare visit.

- Written informed consent will be obtained in conformance with Section 10.3 of this protocol.
- Review of medical history, including prior and concomitant medical conditions, recent vaccinations (≤ 90 days), and significant surgical procedures.
- Review of COVID-19 vaccination status, including number of prior vaccinations, vaccination type, and timing of most recent vaccination.
- Inclusion and exclusion criteria review via participant discussion and medical history review consistent with Section 4.1.1. Specific exclusions to study vaccination will be assessed before any vaccination. Waivers for enrolling participants with exclusions will not be given.
- Demographics, including age, year of birth, sex, race, ethnicity, weight, height, and body mass index (BMI; derived).
- Prior and concomitant medications, including recent and current medications at the time of screening to be reviewed to ensure eligibility criteria are fulfilled (see details in Section 7.4).
- Vital sign measurements, including respiratory rate, blood pressure, pulse rate, pulse oximetry, and temperature (oral or via forehead/ear reader).
- Baseline electrocardiogram (ECG)
- Urine pregnancy test for participants of childbearing potential only. A positive urine pregnancy test at Screening will result in screen failure.

- Physical examination to include head, eyes, ears, nose, and throat (HEENT), neck, lungs, heart, cardiovascular, abdomen, and musculoskeletal system/extremities to allow for study vaccination.
- Assessment of SAEs, starting from the time of informed consent.

6.1.2.2 Day 0 – On-site Study Vaccination

The Screening and Day 0 Visits may be combined whenever feasible. If these visits are not combined, then the following procedures need to be performed and recorded for Day 0. Participant eligibility must be confirmed prior to vaccination.

Prior to study vaccination, all participants with confirmed eligibility will have the following procedures performed:

- Inclusion and exclusion criteria review via participant discussion and medical history review consistent with Section 4.1.1. Specific exclusions to study vaccination will be assessed before any study vaccination.
- Prior and concomitant medications, including recent and current medications to be reviewed to ensure eligibility criteria are fulfilled (see details in Section 7.4).
- Vital sign measurements, including respiratory rate, blood pressure, pulse rate, pulse oximetry, and temperature (oral or via forehead/ear reader). On study vaccination days, vital sign measurements will be collected once before study vaccination to ensure participant has no evidence of fever prior to study vaccination.
- Urine pregnancy test for participants of childbearing potential only. A urine pregnancy test will be performed prior to study vaccination. A positive urine pregnancy test at any time will result in the participant not receiving any further study vaccination.
- Symptom-directed (targeted) physical examination. Physical examination must be done prior to study vaccination.
- Nasal swab (anterior nares) collection for SARS-CoV-2 PCR testing
- Oral swab for SARS-CoV-2 mucosal IgA-mediated hACE2 receptor-binding inhibition assay
- Blood sampling for immunogenicity tests:
 - SARS-CoV-2 (ELISA for anti-S-protein serology).
 - SARS-CoV-2 serostatus (anti-N-protein serology).
 - SARS-CoV-2 NAb assay.
 - Human angiotensin converting enzyme-2 (hACE2) receptor-binding inhibition assay.
- Randomization/Enrollment

At the time of study vaccination, the following procedures will be conducted for all randomized participants:

- Alcohol swab cleansing of the injection sites for study vaccine administration
- Vaccination with study vaccine as an intramuscular (IM) injection.
- Monitoring for any immediate hypersensitivity and anaphylaxis reactions. Participants will remain in clinic for at least 15 minutes post-vaccination for safety monitoring.
- Assessment of unsolicited AEs, MAAEs (all and related to study vaccination), any SAEs, and AESIs (including PIMMCs, myocarditis and/or pericarditis, and complications specific to COVID-19).

Following vaccination, participants will be trained to utilize an eDiary to record reactogenicity. All participants will be asked to record reactogenicity on the day of vaccination and for an additional 6 days after vaccination. Study site personnel should regularly review the eDiary for completeness. Should any reactogenicity event extend beyond 6 days after vaccination (toxicity grade ≥ 1), then it will be recorded using the Continuing Solicited AE form and followed to resolution per ICH guidelines for dataset capture. The toxicology grading scale implemented in the eDiary for the study is included in Appendix 2.

6.1.2.3 Day 28 – In-person/Home Health Care Follow-up Visit (-1 to + 7 Days)

All participants will have the following procedures performed on Day 28:

- Prior and concomitant medications (see details in Section 7.4).
- Oral swab for SARS-CoV-2 mucosal IgA-mediated hACE2 receptor-binding inhibition assay.
- Blood sampling for immunogenicity tests:
 - SARS-CoV-2 (ELISA for anti-S-protein serology).
 - SARS-CoV-2 serostatus (anti-N-protein serology).
 - SARS-CoV-2 NAb assay.
 - hACE2 receptor-binding inhibition assay.
- COVID-19 monitoring and assessment of severity.
- Assessment of unsolicited AEs, MAAEs (all and related to study vaccination), any SAEs, and AESIs (including PIMMCs, myocarditis and/or pericarditis, and complications specific to COVID-19).

6.1.2.4 Day 56 – Phone Follow-up Visit (± 7 Days)

All participants will have the following safety information collected via a remote visit (eg, phone call) on Day 56:

• Prior and concomitant medications (see details in Section 7.4).

- COVID-19 monitoring and assessment of severity
- Assessment of any SAEs, AESIs (including PIMMCs, myocarditis and/or pericarditis, and complications specific to COVID-19), and related MAAEs.

6.1.2.5 Day 90 – In-person/Home Health Care Follow-up Visit (± 7 Days)

All participants will have the following procedures performed on Day 90:

- Prior and concomitant medications (see details in Section 7.4).
- Symptom-directed (targeted) physical examination.
- Blood sampling for immunogenicity tests:
 - SARS-CoV-2 (ELISA for anti-S-protein serology).
 - SARS-CoV-2 serostatus (anti-N-protein serology).
 - SARS-CoV-2 NAb assay.
 - hACE2 receptor-binding inhibition assay.
- COVID-19 monitoring and assessment of severity
- Assessment of any SAEs, AESIs (including PIMMCs, myocarditis and/or pericarditis, and complications specific to COVID-19), and related MAAEs.

6.1.2.6 Day 118 – Phone Follow-up Visit (± 7 Days)

All participants will have the following safety information collected via a remote visit (eg, phone call) on Day 56:

- Prior and concomitant medications (see details in Section 7.4).
- COVID-19 monitoring and assessment of severity
- Assessment of any SAEs, AESIs (including PIMMCs, myocarditis and/or pericarditis, and complications specific to COVID-19), and related MAAEs.

6.1.2.7 Day 146 – Phone Follow-up Visit (± 15 Days)

All participants will have the following safety information collected via a remote visit (eg, phone call) on Day 146:

- Prior and concomitant medications (see details in Section 7.4).
- COVID-19 monitoring and assessment of severity
- Assessment of any SAEs, AESIs (including PIMMCs, myocarditis and/or pericarditis, and complications specific to COVID-19), and related MAAEs.

6.1.2.8 Unscheduled Visit

6.1.2.8.1 General Unscheduled Visit

General Unscheduled Visits not due to respiratory/non-respiratory symptoms suspected to be COVID-19 will be conducted by study personnel for safety follow-up for any participant experiencing a general medical issue while on study. During this visit, the principal investigator may also perform any of the assessments listed in the SOE (Table 1) including blood sample collection, physical assessments, or other optional testing if needed for the clinical evaluation of an AE.

- Prior and concomitant medications (see details in Section 7.4).
- Vital sign measurements, including respiratory rate, blood pressure, pulse rate, pulse oximetry, and temperature (oral or via forehead/ear reader).
- Full physical examination.
- Assessment of unsolicited AEs (only for Unscheduled Visits occurring through 28 days after last study vaccination), MAAEs (only related MAAEs should be recorded if more than 28 days after last vaccination), SAEs, and AESIs (including PIMMCs, myocarditis and/or pericarditis, and complications specific to COVID-19).
- Blood sample collection and other optional testing may be performed during an Unscheduled Visit if directed by the Investigator for clinical evaluation of an AE.

6.1.2.8.2 Unscheduled Visit Due to Suspected COVID-19

In cases of suspected COVID-19 illness where the participant has not been evaluated at an offsite medical facility, they must contact the site within 3 days of symptom onset. If possible, the participant should have an in-person visit to help gather vital signs and do any necessary work up inclusive of physical examination. In cases where the participant has already been at an offsite facility, the site should endeavor to retrieve the visit notes. Only in situations where the participant cannot have an in-person visit should a telehealth visit be planned.

For all telehealth visits:

- Prior and concomitant medications (see details in Section 7.4).
- Nasal swab (anterior nares) collection for SARS-CoV-2 PCR testing
- Assessment of unsolicited AEs (only for Unscheduled Visits occurring through 28 days after last study vaccination), MAAEs (only related MAAEs should be recorded if more than 28 days after last vaccination), SAEs, and AESIs (including PIMMCs, myocarditis and/or pericarditis, and complications specific to COVID-19).

6.1.2.9 Day 180 – End of Study In-person/Home Health Care Visit (± 15 Days)

All participants will have the following procedures performed on End of Study/In-Person Home

Health Care Visit.

- Prior and concomitant medications (see definitions in Section 7.4).
- Vital sign measurements, including respiratory rate, blood pressure, pulse rate, pulse oximetry, and temperature (oral or via forehead/ear reader).
- Symptom-directed (targeted) physical examination.
- Blood sampling for immunogenicity tests:
 - SARS-CoV-2 (ELISA for anti-S-protein serology).
 - SARS-CoV-2 serostatus (anti-N-protein serology).
 - SARS-CoV-2 NAb assay.
 - hACE2 receptor-binding inhibition assay.
- COVID-19 monitoring and assessment of severity
- Assessment of SAEs, AESIs (including PIMMCs, myocarditis and/or pericarditis, and complications specific to COVID-19), and related MAAEs.
- Completion of the EOS form.

6.2 Immunogenicity Assessments

Blood samples will be taken at the time points specified in the procedures above and in the SOEs (Section 1.1) to assess immune response (eg, IgG ELISA for anti-S protein serology, NAb assay, and hACE2 receptor-binding inhibition assay).

Oral swabs will be taken at the time points specified in the procedures above and in the SOEs (Section 1.1) to assess IgA mediated hACE2 receptor-binding inhibition.

hACE2 levels will be obtained at Day 0 and Day 28 from saliva biofluid samples to provide information about the mucosal IgA-mediated antibody response to SARS-CoV-2. The salivary gland epithelial cells express hACE2 and harbor a significant population of IgA-producing plasma cells. Secretory IgA in the saliva has been shown to have potent neutralizing activity against SARS-CoV-2 (Sheikh-Mohammed 2022).

The details on the handling, processing, and shipping of immunogenicity samples will be provided separately in a laboratory manual.

Participants will be asked to provide consent for the use of samples for future testing for assay development related to SARS-CoV-2 or other pathogens. Aliquots of all collected samples from this study may be retained for the stated purposes for a maximum of 25 years (starting from the date at which the last participant had the last study visit), unless local rules, regulations, or guidelines require different time frames or different procedures, in accordance with participant consent.

6.3 Discontinuation or Withdrawal

6.3.1 Individual Participants

6.3.1.1 Withdrawal from Study

Participants are free to withdraw from the study at any time upon request. Participation in the study may be stopped at any time at the discretion of the investigator or at the request of the Sponsor.

Participants may refuse further procedures (including study vaccination) but are encouraged to remain in the study for safety follow-up. In such cases where only safety is being conducted, participant contact could be managed via telemedicine contact (eg, telephone, web chat, video, FaceTime).

Any participant who withdraws from the study prematurely will undergo all EOS assessments at the time of withdrawal. The reason for the early EOS visit must be entered as withdrawal from study on the EOS form.

Vaccination with a non-study, approved or deployed SARS-CoV-2 vaccine alone will not be considered a reason for withdrawal from the study.

6.3.1.2 Replacement of Participants

Participants who sign the ICF but withdraw, are withdrawn or terminated from this study, or are lost to follow up prior to study vaccination may be replaced. Participants who receive study vaccine and subsequently withdraw, are discontinued from additional study visits, are terminated from the study, or are lost to follow-up will not be replaced.

6.3.1.3 Participants Lost to Follow-up

Whenever possible, any participant who withdraws from the study prematurely will undergo all EOS assessments. Any participant who fails to return for final assessments will be contacted by the site in an attempt to have them comply with the protocol.

All reasonable efforts, including contact of emergency contact, must be made to locate participants to determine and report their ongoing status. Lost to follow-up is defined by the inability to reach the participant after a minimum of 3 documented phone calls, text messages, faxes or emails (not performed on the same day), as well as a lack of response by the participant to one registered mail letter. All attempts should be documented in the participant's source documents and/or medical records. If it is determined that the participant has died, the study site will use permissible local methods to obtain the date and cause of death and as much other information as can be obtained, including post-mortem reports.

The status of participants who fail to complete final assessments will be documented in the eCRF. Data that would have been collected at subsequent visits will be considered missing.

6.3.1.4 Study Vaccination Pause Rules

Study vaccination will be paused in the event of reports of 2 or more events of probable or confirmed pericarditis or myocarditis (Table 5), pending review of cases by the Central Cardiac Adjudication Committee that will report the results of their adjudication to the Sponsor to determine whether enrollment may be resumed.

Adverse events meeting any one of the following criteria will result in a hold being placed on subsequent vaccinations pending further review by the Sponsor's Safety Monitoring Committee (SMC):

- One or more participant with an SAE considered related to the investigational vaccine by the investigator and by the Sponsor.
- Three or more participants with grade 3 (severe) single AE preferred term considered related to the investigational vaccine by the investigator and by the Sponsor.

In addition, any SAE assessed as related to vaccine (by study investigator and/or the Sponsor) will be reported to the Sponsor's SMC Chair as soon as possible, and within 24 hours of the Sponsor's awareness of the event. If a pause rule is met, the SMC will conduct a safety review within 48 hours of the identification of AEs meeting the pause rule definition. In addition, the SMC Chair will advise the Clinical Team to advise all sites to immediately pause enrolment and further dosing the study participants. An ad hoc Sponsor's SMC meeting will be convened to review the data and make alternative recommendations. The Sponsor's SMC Charter defines processes for how this review will occur and how the Chair's recommendations will be documented.

The Sponsor, along with medical monitor (Syneos), may request an SMC review for any safety concerns deemed clinically significant that may arise in the trial and not associated with any specific pause rule.

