8 SAFETY MONITORING

The timing and frequency of all safety assessments are listed in the SOE (Section 1.1).

Solicited and unsolicited AEs will be graded for severity using the provided criteria (Appendix 2). Recording of solicited and unsolicited AEs will be conducted by electronic data capture (EDC). AESIs, including PIMMCs, myocarditis and/or pericarditis, and complications specific to COVID-19, will also be monitored (see Appendix 1 for details).

A Central Cardiac Adjudication Committee has been established to adjudicate suspected myocarditis and/or pericarditis cases in the clinical development plan of NVX-CoV2373. Outcomes of the adjudications will be communicated to the Sponsor's Safety Monitoring Committee (SMC).

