- **Causality or relatedness** For each AE/SAE, the investigator must document in the medical notes that they have reviewed the AE/SAE and have provided an assessment of causality as follows.
 - Not Related: There is no reasonable possibility of relationship to study vaccine. The AE does not follow a reasonable temporal sequence from administration of study vaccine or can be reasonably explained by the participant's clinical state or other factors (eg, concurrent diseases, and concomitant medications).
 - Related: There is a reasonable possibility of relationship to study vaccine. The AE follows a reasonable temporal sequence from administration of study vaccine and cannot be reasonably explained by the participant's clinical state or other factors (eg, concurrent diseases or concomitant medications), represents a known reaction to study vaccine or other vaccines in its class, is consistent with the known pharmacological properties of the study vaccine, and/or resolves with discontinuation of the study vaccine (and/or recurs with re-challenge, if applicable).
- Adverse reaction (AR) An AR is any AE caused by an IP.
- Suspected adverse reaction (SAR) An SAR is any AE for which there is a reasonable possibility that the IP caused the AE. For the purposes of investigational new drug (IND) safety reporting, "reasonable possibility" means there is evidence to suggest a causal relationship between the IP and the AE. SAR implies a lesser degree of certainty about causality than AR.
- Unexpected An event is considered unexpected if it is not listed in the IB, is not listed at the specificity or severity that has been observed, or, if an IB is not required or available, is not consistent with the risk information described in the General Investigational Plan or elsewhere in the IND. Unexpected also refers to events that are mentioned in the IB as occurring with a class of IPs or as anticipated from the pharmacological properties of the IP but are not specifically mentioned as occurring with the particular IP under investigation.

- Severity or intensity The severity (or intensity) of an AE/SAE refers to the extent to which it affects the participant's daily activities and will be classified as mild, moderate, or severe using the following criteria:
 - Mild: These events require minimal or no treatment and do not interfere with the participant's daily activities.

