	Histopathologic confirmation of myocarditis ⁴
	• cMRI findings consistent with myocarditis ³ in the presence of troponin level above upper
	limit of normal (any type of troponin)
	AND
	No other identifiable cause of the symptoms and findings
Acute	Presence of ≥ 2 new or worsening of the following clinical features:
	• Acute chest pain ⁶
pericarditis ⁵	Pericardial rub on exam
•	New ST-elevation or PR-depression on ECG
	New or worsening pericardial effusion on echocardiogram or MRI
Myopericarditis	This term may be used for patients who meet criteria for both myocarditis and pericarditis.
Abbreviations: AV	V = atrioventricular; CDC = Centers for Disease Control and Prevention; cMRI = cardiac magnetic

Abbreviations: AV = atrioventricular; CDC = Centers for Disease Control and Prevention; cMRI = cardiac magnetic resonance imaging; ECG = electrocardiogram; ESC = European Society of Cardiology; MRI = magnetic resonance imaging.

1. Persons who lack the listed symptoms but who meet other criteria may be classified as subclinical myocarditis (probable or confirmed).

2. To meet the ECG or rhythm monitoring criterion, a probable case must include at least one of 1) ST-segment or T-wave abnormalities; 2) Paroxysmal or sustained atrial, supraventricular, or ventricular arrhythmias; or 3) AV nodal conduction delays or intraventricular conduction defects.

- 3. Using either the original or the revised Lake Louise criteria (Ferreira 2018).
- 4. Using the Dallas criteria (Aretz 1987). Autopsy cases may be classified as confirmed clinical myocarditis on the basis of meeting histopathologic criteria if no other identifiable cause.
- 5. Based on the 2015 ESC Guidelines for the diagnosis and management of pericardial diseases (Adler 2015). https://academic.oup.com/eurheartj/article/36/42/2921/2293375
- 6. Typically described as pain made worse by lying down, deep inspiration, or cough, and relieved by sitting up or leaning forward, although other types of chest pain might occur.

Adapted from Gargano 2021.

Table 6:Management of Probable or Confirmed Myocarditis, Pericarditis, and
Myopericarditis Cases

Clinical Presentation	Procedures				
Probable or	 ER visit and evaluation by a physician (as per national/local guidelines): Diagnostic work up might include: CBC, Inflammatory markers: ESR, CRP Cardiac markers: Troponin I, BNP, NT-proBNP Chest radiograph V. ECG 				
Confirmed Myocarditis,	2) Evaluation by a cardiologist/pediatric cardiologist (as applicable)				

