Coagulopathy:	Deep vein thrombosis, myocardial infarction, stroke.		
Renal Disorders:	Acute kidney injury.		
Hematologic Disorders:	Thrombocytopenia, septic shock-like syndrome.		
Inflammatory Disorders:	Cytokine Release Syndrome ² related to COVID-19 infection, multisystem inflammatory syndrome in children (MIS-C).		
Neurologic Disorders:	Generalized convulsions.		

 Table 8:
 Adverse Events Representing Complications Specific to COVID-19¹

Abbreviations: ARDS = acute respiratory distress syndrome; COVID-19 = coronavirus disease 2019; DAIDS = Division of AIDS; MedDRA = Medical Dictionary for Regulatory Activities.

- COVID-19 manifestations associated with more severe presentation and decompensation with consideration of enhanced disease potential. The current listing is based on Coalition for Epidemic Preparedness Innovations /Brighton Collaboration Consensus Meeting (12/13 March 2020) and expected to evolve as evidence accumulates (Lambert 2020).
- 2. Cytokine release syndrome is a disorder characterized by nausea, headache, tachycardia, hypotension, rash, and/or shortness of breath (DAIDS 2017).

APPENDIX 2: TOXICITY GRADING SCALE FOR CLINICAL ABNORMALITIES (LOCAL AND GENERAL SYSTEMIC REACTOGENICITY AND VITAL SIGNS)

Table 9:Modified FDA Toxicity Grading Scale for Clinical Abnormalities (Local and
General Systemic Reactogenicity)

Local Reaction to Injectable Product				
	Mild (Grade 1)	Moderate (Grade 2)	Severe (Grade 3)	Potentially Life Threatening (Grade 4)
Pain	Does not interfere with activity	Repeated use of non- prescription pain reliever >24 hours or interferes with activity	Significant; any use of prescription pain reliever or prevents daily activity	Requires ER visit or hospitalization
Tenderness	Mild discomfort to touch	Discomfort with movement	Significant discomfort at rest	Requires ER visit or hospitalization
Erythema/redness ^a	2.5 – 5 cm	5.1 – 10 cm	>10 cm	Necrosis or exfoliative dermatitis ^b
Induration/swelling ^a	2.5 – 5 cm	5.1 – 10 cm	>10 cm	Necrosis ^b
Systemic (General)				
	Mild (Grade 1)	Moderate (Grade 2)	Severe (Grade 3)	Potentially Life Threatening (Grade 4)
Fever ^c (°C) (°F)	38.0 - 38.4 100.4 - 101.1	38.5 - 38.9 101.2 - 102.0	39.0 - 40 102.1 - 104	>40 >104
Nausea/vomiting	Does not interfere with activity or $1-2$ episodes/24 hours	Some interference with activity or >2 episodes/24 hours	Prevents daily activity, or requires IV hydration outside of hospital	Requires ER visit or hospitalization

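### The three-participant pause rule names grade 3 only and does not say how related, non-serious Grade 4 events on the Appendix 2 scales count

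*Protocol*

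**What the plan says.** Protocol Section 6.3.1.4 has three numerical triggers. Vaccination pauses for two or more myocarditis or pericarditis events. It is also held, pending SMC review, after a single related SAE, and for "Three or more participants with grade 3 (severe) single AE preferred term considered related to the investigational vaccine". Both of these last two triggers need investigator and Sponsor to agree that the event is related.

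The same section lets the Sponsor and medical monitor ask for an SMC review of any other safety concern that they consider clinically significant.

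Two severity scales are in force. Section 8 states: "Solicited and unsolicited AEs will be graded for severity using the provided criteria (Appendix 2"). Table 9 (reactogenicity) and Table 10 (vital signs) in that appendix each have four grades. Grade 3 is labelled severe and Grade 4 potentially life-threatening. Section 8.1, by contrast, says that the severity of an AE or SAE "will be classified as mild, moderate, or severe using the following criteria". It has no fourth level, and it refers back to Appendix 2 for specific AEs.

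In Table 9, Grade 4 fever is a temperature above 40 °C, with Grade 3 running from 39.0 to 40 °C. For pain, tenderness, nausea/vomiting, headache, fatigue/malaise, myalgia and arthralgia, Grade 4 reads "Requires ER visit or hospitalization".

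**The concern.** A safety trigger should not become harder to meet as the reactions get worse. This one names a single grade and is silent on the grade above it. Whether a cluster of related Grade 4 reactions stops dosing then depends on whether someone calls an individual case serious, or asks for a review, and not on the rule itself.

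The participants are aged 12 to under 18, and up to 25 sites and the Sponsor must apply the rule in the same way. Once a pause rule is met, the SMC has 48 hours to review. A dispute about whether it has been met should not arise at that moment.

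**Working it through.** No figure in the protocol is in dispute, and no arithmetic beyond counting is needed. The check compares the rule with the grading scales and the SAE definition.

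**Step 1. Which scale does the rule use?** The words grade 3 (severe) match the Table 9 and Table 10 column headed severe, Grade 3. Section 8.1 uses no grade numbers. Elsewhere the protocol writes an inclusive threshold when it means one: Sections 6.1.1.1 and 6.1.2.2 follow reactions of toxicity grade ≥ 1 that outlast the diary period. Section 6.3.1.4 has no such sign.

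**Step 2. Is a Grade 4 event always an SAE?** Table 9 has ten items.

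- Seven reach Grade 4 through a required ER visit or hospitalization.
- One (fever) reaches it on temperature alone.
- Two (erythema, induration) reach it through necrosis or, for erythema, exfoliative dermatitis.

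The Section 8.1 SAE definition asks for death, immediate risk of death, inpatient hospitalization (in general detention in a hospital or emergency ward, usually overnight), lasting incapacity, a congenital anomaly, or an important medical event by judgment. It expressly leaves out events that would have threatened life only if they had been worse. A fever above 40 °C managed at home, or a headache that needs an ER visit with same-day discharge, can therefore be Grade 4 without being an SAE. That is possible for 7 + 1 = 8 of the ten items.

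**Step 3. Apply the rule literally.** All events below are the same preferred term and are judged related by investigator and Sponsor.

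| Participants' events | Counted at grade 3 | Related SAEs | Hold? |
|---|---|---|---|
| Three fevers of 39.0 to 40 °C, none serious | 3 | 0 | Yes |
| Three fevers above 40 °C, none serious | 0 | 0 | No |
| Two grade 3 and one Grade 4, none serious | 2 | 0 | No |
| Three fevers above 40 °C, one judged serious | 0 | 1 | Yes, by the SAE criterion |

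The second row is worse than the first but gives no hold. The third has the same number of participants as the first, one of them more severely affected, and gives no hold.

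**Step 4. What if a reaction passes through grade 3 on its way to Grade 4?** Section 8.1 says that the most intense severity is the one reported when severity changes. Section 8.2 says that a change of severity requires a new AE record. Take three participants whose related, non-serious fever rises from the 39.0 to 40 °C band to above 40 °C. If only the most intense severity is kept, the grade 3 count is 0. If the earlier records stand, it is 3. The same cases give opposite answers.

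**The case against.** The strongest reply is that the intent is clear and the gap narrow. Much of that stands.

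- **The gravest events are covered.** A reader might infer that the most severe reactions never stop dosing. The protocol does not support that. One related SAE is enough for a hold, an event is serious in the view of either investigator or Sponsor, and the definition reaches emergency-ward detention and important medical events, with an ER-treated example.
- **This is not the only numerical brake.** A reader might take it as such, but Section 6.3.1.4 also counts related SAEs (one) and cardiac events (two). The rule examined here is the automatic trigger for clusters of non-serious, non-cardiac events.
- **The gap is limited to Appendix 2 items.** Tables 9 and 10 grade only listed reactogenicity symptoms and vital signs. Other AEs fall on the Section 8.1 scale, where severe is the top level, so nothing can lie above it. The word severe in the rule could be read in that sense, but that does not explain the words grade 3.
- **Not every ER visit is Grade 4.** Table 9 speaks of a symptom that requires one, and fever, erythema and induration have other criteria.
- **There is a backstop.** The SMC review on request is real, but it is discretionary and is not an automatic hold.
- **The reach in time is short.** Each participant receives one dose, so a hold affects only those not yet vaccinated.

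These points narrow the concern. None of them tells a site how to count a related, non-serious Grade 4 event.

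**Conclusion.** The point holds within a defined scope: related Grade 4 events on the Appendix 2 scales that do not meet the SAE definition. For those events the rule, followed literally, is not monotone in severity, and the conflict between Sections 8.1 and 8.2 makes the count depend on which recording instruction a site follows.

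This conclusion rests on the literal wording and on the premise that some Grade 4 events will not be judged serious, which the protocol's own definitions allow. The drafters may well have meant otherwise, but the text does not say so. The protocol gives no expected rates of grade 3 or Grade 4 events, so no probability of a missed hold can be derived from it, and none is claimed. The matter is a wording defect in a safety rule that should be corrected. It does not affect the planned analyses.

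**What to change.** Reconcile Section 6.3.1.4 with Appendix 2 (Tables 9 and 10) and with the three-level severity scale in Section 8.1. The pause rule should then state which scale applies and how Appendix 2 Grade 4 events count. Reconcile Sections 8.1 and 8.2 on whether an earlier grade 3 record is kept when an event worsens. Carry the same wording into the SMC charter. The clinical threshold itself is for the sponsor and the SMC to decide.

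The cost is one or two sentences in the protocol and the charter. The downside is at most a slightly more frequent hold.
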